6.3.2. Laboratory Data

To determine if there are any clinically significant laboratory abnormalities, the safety laboratory tests will be assessed against the criteria specified in the protocol. The assessment will consider whether each participant's baseline test result is within or outside the laboratory reference range for the laboratory parameter. Absolute value, changes from baseline and percent changes from baseline in laboratory data will be summarized. The number (%) of subjects with abnormal AST, ALT, and alkaline phosphatase ($>2 \times$ ULN), and bilirubin ($>1.5 \times$ ULN) and the number (%) of subjects with abnormal AST, ALT, and alkaline phosphatase ($>2 \times$ baseline) will also be presented. Baseline of safety laboratory tests will be the last pre-dose measurement.

6.3.3. Vital Signs

Vital signs will be summarized for treatment arm in accordance with the Pfizer reporting standards.

[figure not shown]
6.3.4. Physical Examination

Physical examination data (including incidence of clinically significant changes in physical examination from baseline) will be summarized for treatment arm in accordance with the Pfizer reporting standards.

6.3.5. Electrocardiogram Analyses

Parameters of electrocardiogram analyses (including PR, QRS, QT, QT_C) will be summarized according to Pfizer's reporting standards.

CCI

6.5. Analysis of PD and Biomarker Endpoints

Concentrations of ACPA, RF, IP-10, hsCRP, and ESR will be analyzed using E1 and D1 methods. The log-transformation of the endpoints will be explored if needed for achievement symmetry of the distributions

6.6. Analysis of MRI Endpoints

Each of the 37 endpoints listed in [Section 3.1.4](#) will be analyzed by the E1 and D1 methods. The log-transformation of the endpoints will be explored if needed for achievement symmetry of the distributions.

6.7. Additional Analyses

For the E1 analysis of DAS28-CRP at week 12, analyses E2 and E3 for the ratio and difference of DAS28-CRP remission rates at week 24 and E3 analyses of ACR 20, ACR 50, ACR 70 and ACR 90 responder rates at week 24 we may implement additional comparisons.

- A comparison of the treatment effect between the combination treatment arm PF-06650833 +TOFACITINIB and monotherapy arm PF-06650833 and the comparison of the combination arm PF-06650833 + PF06651600 with each of the mono-therapy treatment arms (PF-06650833 and PF06651600).
- An estimation of the treatment effects of primary interest (each of the combination treatment arms versus tofacitinib) for the subset of anti-TNF naïve patients.

Also, for each of the visits and treatment arms we will estimate the proportions of subjects in the mITT data set that were removed from the sensitivity data set because of the potential influence on these observations of poor compliance , use of prohibited concomitant medication or any of these reasons. The Blyth-Still-Casella method will be used for the estimation.

7. INTERIM ANALYSES

One or more interim analyses (IA) may be performed for internal business decision-making or sample size re-estimation (there is no intention a priori to terminate the study or a treatment arm based on the results of the IA). The final number and timing of any IA, if performed, will be defined by the sponsor.

If an IA is performed, an Interim Analysis Committee/Executive Committee will be constituted that will include members of senior Pfizer leadership. Before any interim analysis is initiated, the details of the objectives, decision criteria, dissemination plan, and method of maintaining the study blind as per Pfizer's SOPs will be documented and approved in an Interim Analysis Committee/Executive Committee charter. In addition, the analysis details must be documented and approved in an interim analysis SAP or final SAP. The study team will remain blinded to all interim results.

7.1.1. Data Monitoring Committee

An Independent Oversight Committee (IOC) will be constituted and be responsible for review of unblinded safety and laboratory data on a regularly scheduled, periodic basis (eg, after 25%, 50% and 75% of participants have been randomized, and periodically thereafter), as well as on an ad hoc basis at the request of the study team. The IOC may also have access to unblinded efficacy data from any interim analyses (if performed) for ongoing assessment of overall benefit: risk. For this study, the IOC will be an Internal Review Committee (IRC) comprised of Sponsor personnel (at least one of whom is medically qualified and one of whom is a clinical statistician) not directly involved in study conduct or in interactions with site personnel or participants.

The IRC will be responsible for ongoing monitoring of safety of participants in the study according to the Charter. Any recommendations made by the IRC to alter the conduct of the study will be forwarded to the Executive Committee for final decisions. Pfizer will forward such decisions, which may include summaries of aggregate analyses of endpoint events and of safety data that are not endpoints, to regulatory authorities, as appropriate.

9. APPENDICES

9.1. Appendix 1. Definition and Use of Visit Windows in Reporting

Visit windows will be used for efficacy variables, and for any safety data that display/summarize by study visit. For other endpoints (eg, vital signs, physical examinations), visit windows will be applied for summary statistics by study visits if required.

Table 12. Definition of Visit Windows

[figure not shown]
Visit Label	Target Day	Definition [Day window]
Screening		Days -28 to Day 0
Baseline	Day 1, Baseline	Day 1
Week 2	15	Days 2 to 22
Week 4	29	Days 23 to 43
Week 8	57	Days 44 to 71
Week 12	85	Days 72 to 99
Week 16	113	Days 100 to 127
Week 20	141	Days 128 to 155
Week 24	169	Days 156 to 183
Follow Up/End of Study		
Week 28		Days 184 to -

For the lab values, if the calculated study day for the labelled baseline visit is not study Day 1 but falls within 28 days before the start of the study dosing, then that data should be used for the baseline instead of leaving baseline missing.

[figure not shown]
For the other values, if the calculated study day for the labelled baseline visit is not study Day 1, but falls before the start of the study dosing, then that data should be used for the baseline instead of leaving baseline missing.

If two or more visits fall into the same window, keep the one closest to the Target Day. If two visits are equaled distant from the Target Day in absolute value, the later visit should be used.

[figure not shown]
CCI

CCI

CCI

CCI

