
 To assess the safety of PF-06650833, PF-06651600, and tofacitinib alone and of the combinations of PF-06650833 with PF-06651600 and tofacitinib 	
Most of the safety outcomes are defined by the Sponsor's standards. These outcomes include
 
 Incidence and severity of adverse events (AEs), serious adverse events (SAEs), and withdrawals due to adverse events. Change from baseline in clinical laboratory values (chemistry, hematology parameters). Change from baseline in vital signs (blood pressure, pulse rate and temperature measurements),ECG-based parameters. Incidences of severe and opportunistic infection AEs; herpes virus infection AEs; clinically significant categorical increases in hepatic enzymes Aspartate aminotransferase (AST), and Alanine aminotransferase (ALT) and total bilirubin, and potential cases meeting Hy's Law criteria for increased risk of drug-induced liver injury (DILI); major adverse cardiovascular events (MACE), including pulmonary embolism (PE) and deep vein thrombosis (DVT), Cerebrovascular accident (CVA); Adverse events (AEs) for decreased renal function, acute kidney injury, clinically significant increases in serum creatinine (Scr) and decreases in 	
 There is no defined estimand for these endpoints. They will be analyzed using Pfizer data standards as applicable.

	
estimated glomerular filtration rate (eGFR).
 
The additions include the parameters of the audiology test
	
Secondary	Secondary	Secondary

 • To explore other signs of clinical efficacy of all treatment arms at week 12 and 24 	
 • Change from baseline in DAS28-CRP at week 24. • Change from baseline in Tender/Painful and Swollen Joint Count at Week 12 and Week 24. • Change from baseline in Physician's Global Assessment (PhGA) of Arthritis at Week 12 and Week 24. • American College of Rheumatology (ACR 20, ACR 50, ACR 70, and ACR 90) responder rates at Week 12 and Week 24. 	
 • E1 for continuous endpoints. • E3 for binary endpoints.

CCI

CCI

CCI		

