Up to approximately 450 participants are planned to be randomized globally into the study to ensure at least up to approximately 370 participants complete at least 12 weeks of active dosing (assuming a dropout rate of approximately 18%). Participants will be in this study for a total of approximately 32 weeks which includes an up to 28-day screening period, a 24-week active treatment period, and a 4-week drug-free follow-up period.

Figure 1. Study Design Schematic

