4. ANALYSIS SETS

For purposes of analysis, the following analysis sets are defined.

Table 7. Analysis Sets

Data Set	Description
Modified Intent to Treat (mITT)	All participants randomly assigned to investigational product who take at least 1 dose of investigational product. Participants will be analysed according to the randomized intervention.
Sensitivity Set (SNS)	All participants randomly assigned to investigational product who take at least 1 dose of investigational product. It is a subset of mITT data set where the observations that may be affected by the poor compliance or use of concomitant medications are excluded. Participants will be analysed according to the randomized intervention.
Safety Set	All participants randomly assigned to investigational product who take at least 1 dose of investigational product. Participants will be analysed according to the intervention they actually received.

CCI

PD Data Set (PD)	All participants randomly assigned to investigational product and who take at least 1 dose of investigational product and have at least 1 of PD parameters of interest.
------------------	---

Appendix 1 shows how to assign observations to the discrete set of study visits based on the observation time. CCI

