5.4. Analysis of Safety Data

Safety data will be summarized based on observed-case data by treatment arm.

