6.3. Safety Summaries and Analyses

All safety analyses will be performed on the safety analysis set population ([Section 4](#)).

The safety data will be summarized in accordance with Pfizer Data Standards. All safety data will be summarized descriptively through appropriate data tabulations, descriptive statistics, categorical summaries, and graphical presentations.

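### As readable, SAP Table 12 labels visits by study day alone, so in by-visit laboratory summaries the drug-free follow-up visit of a participant who stops by about Day 155 is usually counted as a treatment week.

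*SAP*

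**What the plan says.** SAP section 4 makes study day the basis for labelling: "Appendix 1 shows how to assign observations to the discrete set of study visits based on the observation time". Appendix 1 sets the scope: "Visit windows will be used for efficacy variables, and for any safety data that display/summarize by study visit". In Table 12, Week 16 is Days 100 to 127, Week 20 is Days 128 to 155, Week 24 is Days 156 to 183, and Week 28, under the Follow Up/End of Study line, starts at Day 184. When visits collide, the rule is: "If two or more visits fall into the same window, keep the one closest to the Target Day"; a tie goes to the later visit. Appendix 1 makes an exception for a labelled baseline visit that is not on Day 1. It has no readable counterpart for a labelled follow-up visit.

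SAP section 2.2 separates "a 24-week active treatment period, and a 4-week drug-free follow-up period". On laboratory data, section 6.3.2 says "Absolute value, changes from baseline and percent changes from baseline in laboratory data will be summarized", section 5.4 says "Safety data will be summarized based on observed-case data by treatment arm", and section 6.3 says "The safety data will be summarized in accordance with Pfizer Data Standards". For the safety endpoints, Table 3 says "There is no defined estimand for these endpoints. They will be analyzed using Pfizer data standards as applicable".

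In the protocol, section 7.1 requires a 4-week follow-up period after permanent discontinuation. Section 8.11 sends participants without an ACR20 response from Week 12 onward to the FU/EOS visit. The Schedule of Activities marks chemistry, hematology and urinalysis at that visit.

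**The concern.** The FU/EOS visit is the same event for everyone: a visit about 4 weeks after the last dose. Under a day-only rule its label depends on when treatment stopped. A completer's visit is Week 28; an early stopper's visit is usually a treatment week. Week 12, when ACR20 non-responders begin to be stopped, is a planned stopping point, so this is not an edge case.

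Change from baseline in laboratory values is a secondary safety endpoint. A by-week row could mix on-drug values with values about 4 weeks off drug. Some of those would come after other RA treatment had begun or after methotrexate had restarted, which protocol section 6.5.4.1 allows from 14 days after the last dose. Protocol section 2.2.5.3 says laboratory changes on tofacitinib characteristically recover after stopping. It gives no timing, and the protocol makes no such statement for the other two drugs. Off-drug values would tend to dilute a reversible change, but restarted therapy could move values either way. Meanwhile the follow-up row would hold almost only completers.

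**Working it through.** **Inputs.** Target days and windows: SAP Table 12. Follow-up about 28 days after last dose, tolerance 3 days: protocol Schedule of Activities. Last planned dosing day: about Day 168. Numbers randomized and completing 12 weeks: protocol 4.1 and SAP 2.2.

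**Reproducing Table 12.** Each upper limit is the midpoint of adjacent target days, with follow-up targeted at 169 + 28 = 197. For example, (85 + 113)/2 = 99 and (169 + 197)/2 = 183. All seven limits (22, 43, 71, 99, 127, 155, 183) match, so the follow-up window is built around a completer.

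**Label of an FU/EOS visit at last dose + 28.**

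| Last dose (day) | Label of FU/EOS visit |
|---|---|
| 1–15 | Week 4 |
| 16–43 | Week 8 |
| 44–71 | Week 12 |
| 72–99 | Week 16 |
| 100–127 | Week 20 |
| 128–155 | Week 24 |
| 156–168 | Week 28 |

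The limit is 183 − 28 = Day 155. With gaps of 31 and 25 days it is 183 − 31 = 152 and 183 − 25 = 158. Thus 155 of 168 possible last-dose days give a treatment-week label. This counts calendar days, not participants.

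**Stops at scheduled visits.** Allow the visit to move by 3 days and the gap to run from 25 to 31 days (7 × 7 = 49 combinations each).
- Week 12 stop: Days 107–119, inside Week 16 (100–127).
- Week 16 stop: Days 135–147, inside Week 20 (128–155).
- Week 20 stop: Days 163–175, inside Week 24 (156–183).

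All 49 combinations fall in the named window in each case.

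**Does the closest-to-target rule remove these records?** It can act only when two visits share a window, and the treatment windows are 21 or 28 days wide.
- Gap of 28 days, on-drug visit on the last-dose day: no last-dose day puts both in one window, so none of the 155 follow-up records is dropped.
- Gap of 25 days, same assumption: 15 of 158 last-dose days share a window and the follow-up record is dropped in 10. Example: last dose Day 45, follow-up Day 70, both in Week 8 (target 57). The distances are 12 and 13, so the earlier visit is kept.
- Gap of 28 days, early-withdrawal visit 8 days after last dose (protocol 6.4 withdraws treatment after an interruption of more than 7 days): 41 of 155 share a window. The follow-up record is dropped in 21 and displaces the early-withdrawal record in 20, so it is used in 155 − 21 = 134.

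**Scale.** 450 − 370 = 80 stops before 12 weeks (450 × 0.18 = 81). With a last dose by Day 84, follow-up falls by Day 84 + 31 = 115, which is Week 16 at the latest. At an assumed 25%, 50% or 75% attendance, 80 stops give 20, 40 or 60 records; the documents support none of these rates. ACR20 stops from Week 12 come on top, and no rate is given for them.

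**The case against.** The strongest reply is that the rule may exist where it cannot be seen. Redactions follow both the section 4 sentence and the Table 12 conventions. The Follow Up/End of Study line has no window of its own as extracted and could be a heading or a nominal label. Safety output also follows sponsor data standards that are not in the documents. This stands as a limit: a reader might infer that the plan has no handling for early follow-up visits, and the documents do not support that. They show only that the readable rule, applied literally, gives this result.

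A second reply concerns attendance. Footnote b of the Schedule of Activities leaves the return visit after early withdrawal to the investigator's medical judgment. Section 7.2 describes discontinuation from the study at the early-withdrawal visit, and follow-up to resolution after stops for adverse events. Section 8.11 does the same for liver, hematology and infection withdrawals, with no stated 4-week visit. The 18% dropout is itself an upper expectation (protocol 9.2.1). This also stands, so 80 cannot be read as a count of mislabelled records, nor 155 of 168 as the share of early stoppers affected.

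Third, section 6.3.2 does not itself say that laboratory summaries are by visit, and having no estimand does not by itself imply an on-treatment target. Both are correct. The point therefore applies only where data are displayed by visit. It rests on the SAP's own division between treatment and drug-free follow-up, not on an assumed estimand.

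Finally, other safety review is untouched: adverse event incidence, participant listings, adjudication of liver-enzyme events and the committee's unblinded laboratory review. That limits the consequences but does not correct the row labels.

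**Conclusion.** The point holds for the text as readable, with medium confidence. Where laboratory data are summarized by study visit, an FU/EOS visit attended about 4 weeks after a last dose on or before about Day 155 (152 to 158 with tolerance) is usually labelled as a treatment week. For stops at the Week 12, 16 or 20 visit this is so under every tolerance combination. The closest-to-target rule drops a minority of these records in the scenarios checked: none, 10 of 158 and 21 of 155 last-dose days.

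The number of records is not derivable; about 80 is a ceiling for stops before Week 12. It is tempting to infer that laboratory toxicity will be understated or an arm comparison distorted. The documents give neither the size nor the direction of any effect, so that inference is not supported. The treatment-policy efficacy analyses, scheduled lipids and ECGs, and adverse event incidence are not affected. The change is worth making because it is cheap and the affected rows describe a secondary safety endpoint, but no primary or key secondary conclusion depends on it.

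**What to change.** In SAP Appendix 1, state that records collected at the nominal FU/EOS visit keep that label whatever the study day, are not eligible for the Week 2 to Week 24 windows, and are summarized in a separate follow-up row. Flag early-withdrawal and unscheduled laboratory values taken after the last dose, so that by-week rows can also be shown on-treatment. If the redacted text or the sponsor's data standards already contain such a rule, cite it and make Table 12 agree.

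The cost is one sentence and one programming flag. The downside is slightly fewer observations in the later by-week rows.

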1.3. Schedule of Activities (SoA)

The SoA table provides an overview of the protocol visits and procedures. Refer to the **STUDY ASSESSMENTS AND PROCEDURES** section of the protocol for detailed information on each procedure and assessment required for compliance with the protocol.

The investigator may schedule visits (unplanned visits) in addition to those listed in the SoA table, in order to conduct evaluations or assessments required to protect the well-being of the participant.

Protocol Activity	Screening	Treatment Period									FU ^b /EOS	EW ^b
Visit Identifier	1	2	3	4	5	6	7	8	9	10		
Study Day/Week ^a	Screening	Day 1/ Baseline	Day 15 ±2	Day 29 ±2	Day 57 ±3	Day 85 ±3	Day 113 ±3	Day 141 ±3	Day 169 End of Treatment ±3	Follow-up ^b ±3		
	Days -28 to 0	Week 0	Week 2	Week 4	Week 8	Week 12	Week 16	Week 20	Week 24	Week 28		
Informed consent	X											
Inclusion/Exclusion Criteria	X	X										
Demographics	X											
RA history, Prior RA medications ^c	X											
Medical history and prior non RA medication history ^d	X											
Height	X											
Weight	X						X			X		
Vital Signs (Pulse, blood pressure), temperature ^e	X	X	X	X	X	X ^e	X	X	X	X	X	
Complete Physical Examination ^f	X									X		X
Targeted Physical Examination ^f		X	X	X	X	X	X	X		X		
ECG (12 lead) ^g	X	X	X	X	X	X				X		X
Chest radiograph ^h	X											
Audiogram ^w	X									X		X
Magnetic resonance imaging (MRI) of hand ^x	X					X				X		
Laboratory Evaluations												
Blood chemistry (fasting), Hematology ⁱ	X	X	X	X	X	X	X	X	X	X	X	X

CCI

Protocol Activity	Screening	Treatment Period								FU ^b /EOS	EW ^b
Visit Identifier	1	2	3	4	5	6	7	8	9	10	
Study Day/Week ^a	Screening	Day 1/ Baseline	Day 15 ±2	Day 29 ±2	Day 57 ±3	Day 85 ±3	Day 113 ±3	Day 141 ±3	Day 169 End of Treatment ±3	Follow-up ^b ±3	
	Days -28 to 0	Week 0	Week 2	Week 4	Week 8	Week 12	Week 16	Week 20	Week 24	Week 28	

CCI

Blood sample for viral surveillance		X		X		X			X		
Urinalysis (including, protein creatinine, pH color, clarity, specific gravity) with microscopy (to be processed at central lab) ^{j,k}	X	X	X	X	X	X	X	X	X	X	X
Urine pregnancy test ^l	X	X	X	X	X	X	X	X	X	X	X
Contraception check ^m	X	X	X	X	X	X	X	X	X	X	X
Serum FSH (WONCBP only)	X										
HBsAg, HbcAb, HBsAB and HCVAb ⁿ	X										
HIV testing ^o	X										
Tuberculosis test ^p	X										
Banked biospecimen (whole blood, prep R1) for potential exploratory RNA Analysis		X	X			X			X		

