- s. If the absolute neutrophil count (ANC) is $\leq 1500/\text{mm}^3$ at Screening, and the participant is eligible to enter the study, the ANC counts will need to be repeated (once) prior to the randomization visit, and the ANC must be $\geq 1500/\text{mm}^3$ for the participant to be eligible for randomization. A delay (< 2 Weeks) in randomization for repeating labs will not be considered a protocol deviation.
- t. Investigational product tablets will be administered to the participant in the clinic on the morning of clinic visits and all other dosing will be performed by the participant outside of the clinic.

PFIZER CONFIDENTIAL

CCI

- w. Audiograms may be performed within a ± 2 -week window relative to the study visit.
- x. MRIs, if performed, will be conducted in a subgroup of participants. Participants in the MRI subgroup will be recruited globally in the order of enrollment in the IVRS up to a maximum number as defined by the sponsor. Participants who refuse to undergo MRI may still be eligible for enrollment into the study. Baseline MRIs should be acquired after all other eligibility criteria have been met and at least 1 week prior to randomization. After randomization, MRIs will be performed at Visit 6/Week 12 (± 1 week), and Visit 9/Week 24 (-2 to +1 week). A delay in acquisition of the Baseline MRI up to 1 week (7 days) after Randomization at Visit 2 (Week 0, Day 1) solely due to scheduling availability will not be considered a protocol deviation (PD).
- y. Additional sample will be collected upon presentation of infection.

PFIZER CONFIDENTIAL

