8.2.7. Audiogram

All participants will have an audiogram at times specified in the **SoA**. Audiograms may be performed within a ± 2 week window relative to the study visit. When possible, the participant should have the audiogram performed at the same evaluation center during the study. Audiogram should be performed at the Early Termination (ET) visit unless the previous audiogram was less than 16 weeks prior to this.

If there is a clinically meaningful, treatment related decline in hearing from baseline screening the subject will be followed off treatment with appropriate testing at regular intervals, until hearing returns to baseline (prior to the participant's receiving the investigational product) or is determined to be clinically stable.

The information from the audiogram will be entered into the data collection tool.

Any de-identified audiogram results/reports and any additional relevant test results (if applicable) may be requested to be forwarded to Pfizer (and/or designee) at any time during the study. Further details will be provided to investigators prior to the start of the study.

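### Table 12 of the SAP starts Week 24 at Day 156, so a Week 24 hand MRI done at the protocol's early limit is assigned to Week 20; audiograms can be affected in the same way

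*SAP*

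**What the plan says.** **Protocol.** The schedule of activities (Section 1.3) sets the Week 24 visit at "Day 169 End of Treatment ±3", that is Days 166 to 172. Footnote x gives the follow-up MRI times, ending "and Visit 9/Week 24 (-2 to +1 week"; Section 8.1.5 repeats this range and says that the imaging guidelines take precedence over the schedule for these procedures. After baseline, MRI is planned only at Weeks 12 and 24. Section 8.2.7 allows audiograms in a ±2 "week window relative to the study visit".

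**SAP.** Section 4 states: "Appendix 1 shows how to assign observations to the discrete set of study visits based on the observation time". In Section 9.1, Table 12 gives Week 20 as "Days 128 to 155", Week 24 as "Days 156 to 183" and Week 28 as Day 184 onward. The scope is: "Visit windows will be used for efficacy variables, and for any safety data that display/summarize by study visit". Section 3.1 lists imaging as one of four classes of efficacy outcome, so MRI is in scope. Section 6.6 says that each of the 37 MRI endpoints "will be analyzed by the E1 and D1 methods". Per Section 5.2, E1 is an MMRM with treatment-by-visit terms and an unstructured covariance matrix, and D1 is descriptive. Audiology is named among the safety outcomes in Section 3.3, but no by-visit audiology table is described.

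The readable SAP has no separate window for MRI or audiograms and no rule to keep the nominal visit.

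**The concern.** The protocol gives these two assessments wider tolerances than an ordinary visit, and for MRI the early side is the wider one. Table 12 was built for visits four weeks apart and cuts at the midpoint, which is where the early MRI limit falls. A site that follows the protocol can therefore produce a valid end-of-treatment scan that the SAP labels Week 20.

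Two things are at stake. First, the value leaves the Week 24 descriptive summary, which uses only data assigned to that visit. Second, a few relabelled scans would add an unplanned visit to the MRI model. A participant with a single end-of-treatment scan contributes to Week 20 or to Week 24, never to both. If the Week 20 level stays in the model, no data inform the Week 20 to Week 24 covariance. The fit can then run into trouble that goes beyond the few scans involved, and the readable SAP gives no fallback.

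**Working it through.** **Inputs.** Table 12 targets: Days 113, 141 and 169 for Weeks 16, 20 and 24. Week 24 visit: Days 166 to 172. MRI offset: −14 to +7 days. Audiogram offset: −14 to +14 days. Assumptions: the Week 28 target, which Table 12 leaves blank, is Day 197; and the end-of-treatment audiogram is due at Week 24. The extracted schedule is broken, but the audiogram mark lines up with the Week 24 MRI mark.

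**Reproducing Table 12.** Each window ends at the midpoint with the next target.
- Week 16 ends at (113 + 141)/2 = 127, so Week 20 starts at Day 128.
- Week 20 ends at (141 + 169)/2 = 155, so Week 24 starts at Day 156.
- Week 24 ends at (169 + 197)/2 = 183, so Week 28 starts at Day 184.

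These match the SAP.

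**Reading A: tolerance counted from nominal Day 169.**
- MRI: 169 − 14 = 155 to 169 + 7 = 176. One of 22 days (Day 155) is in Week 20; none is in Week 28.
- Audiogram: 155 to 169 + 14 = 183. One of 29 days (Day 155) is in Week 20; none is in Week 28.

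**Reading B: tolerance counted from the actual visit.** Allowed days become 166 − 14 = 152 to 172 + 7 = 179 for MRI, and 152 to 172 + 14 = 186 for audiograms.

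| Visit day | Allowed days in Week 20 (both tests) | Allowed days in Week 28 (audiogram only) |
|---|---|---|
| 166 | 152–155 (4) | 0 |
| 167 | 153–155 (3) | 0 |
| 168 | 154–155 (2) | 0 |
| 169 | 155 (1) | 0 |
| 170 | 0 | 184 (1) |
| 171 | 0 | 184–185 (2) |
| 172 | 0 | 184–186 (3) |
| Total | 10 | 6 |

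- MRI: 7 visit days × 22 offsets = 154 pairs; 10/154 = 6.5%.
- Audiogram: 7 × 29 = 203 pairs; (10 + 6)/203 = 16/203 = 7.9%.
- For a visit on Day 166 alone, 4 of 22 MRI days (18%) are relabelled.

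**Week 12 check.** The MRI tolerance there is ±1 week. Even from a visit on Days 82 to 88, scans fall on 82 − 7 = 75 to 88 + 7 = 95, inside Table 12's Days 72 to 99. The mismatch is specific to Week 24.

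**Endpoints exposed.** SAP Section 3.1.4 gives 20 DCE-MRI + 9 RAMRIS + 8 RAMRIQ = 37 endpoints. All use the same scan date, so one relabelled scan moves all of that participant's Week 24 MRI values.

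**The case against.** The best case against has four parts.

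1. **It is an edge effect.** A reader might infer that compliant Week 24 tests generally miss the window. They do not: on the nominal reading only Day 155 is affected, and on either reading most allowed dates stay in Week 24. Nor can an allowed MRI reach Week 28, since the latest is Day 179. This stands and limits the point.

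2. **The wider MRI range is one reading of two.** Footnote x does not say whether its tolerance counts from Day 169 or from the actual visit, and the imaging guidelines that take precedence are a separate document. The 6.5% and 18% figures need the second reading. This stands for those figures. Day 155 needs no such choice, because it is exactly two weeks before the target. For audiograms the protocol does tie the tolerance to the study visit.

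3. **The model problem is conditional.** It is tempting to say that the covariance fails for all 37 MRI endpoints. That needs at least one relabelled scan and a Week 20 level kept in the fit. The SAP's list of tables shows a table of MMRM input parameters (Table 13) that is not readable, and parts of Appendix 1 are redacted, so the visits used may be fixed there. The claim holds only as a conditional one.

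4. **The audiogram effect is conditional.** Table 12 governs safety data only where they are shown by visit, and no such audiology summary is described. This also stands.

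None of this removes the mismatch: applying the readable rule to an MRI at the protocol's own limit gives Week 20.

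**Conclusion.** The point holds as a narrow mismatch between the two documents. A compliant Week 24 MRI on Day 155, or on Days 152 to 155 if counted from a visit on Days 166 to 169, is assigned to Week 20. Audiograms share this if they are summarised by visit, and those on Days 184 to 186 after a late visit go to Week 28.

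The affected share is 0% if tests are done on the visit day and about 6 to 8% if visit days and offsets are uniform and counted from the actual visit. The uniform timing is an assumption with no support in the documents. These shares count calendar days and do not forecast patient numbers. Applied to the protocol's ceiling of about 60 MRI participants per arm, 6.5% is about 4 scans (60 × 0.065 = 3.9) before dropout.

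A reader might conclude that the data are lost. They are not: the values stay in the database under another label. The MRI is an optional, exploratory component in a subset, the audiogram is a safety test, and the primary and key secondary endpoints are not touched. This is a minor correction, worth making because it is cheap and the rule as written misassigns compliant data.

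**What to change.** Add to SAP Section 9.1:

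- MRI and audiogram results obtained within the protocol window for a scheduled assessment keep that nominal visit.
- All other MRI and audiogram results follow Table 12. This part is needed so that a Week 12 scan on Day 97, a Week 24 scan on Day 181 or an early-withdrawal audiogram still has a rule.
- The MRI MMRM includes only the planned Week 12 and Week 24 visits.

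The text should also say whether the MRI tolerance counts from Day 169 or from the actual visit. With the nominal-visit rule, no protocol-compliant date falls outside Week 24.

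The cost is a few lines of SAP text and a small programming change, with no effect on study conduct. If the redacted SAP text or the imaging guidelines already contain such a rule, the sponsor need only confirm it.
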